#### **9.2.4 Other Analyses**

##### **9.2.4.1 Biomarker Exploratory Analyses**

The biomarker analyses of the present study will be exploratory and primarily make use of descriptive statistical methods. For continuous variables, descriptive statistics including the mean, standard deviation, median, minimum and maximum values will be provided. Categorical variables will be summarized by numbers and proportions (if possible, the 95% confidence intervals will be calculated).

Appropriate statistical methods will be used to investigate any possible relationship of biological subtypes/profiles and biomarker levels with the efficacy end-points and outcome, and to compare with data from healthy volunteers (if available). Any exploratory biomarker analyses, including additional sensitivity analyses, will be outlined in the specific statistical analysis plan/summary.

#### **9.2.5 Other Subgroup Analyses**

Other exploratory subgroup analyses may be performed if deemed appropriate.

### 9.2.6 Second Course Phase Analyses

Exploratory second course phase analyses may be performed if deemed appropriate.

## 10. TABLES Y FIGURES

Table/Figure No.	Title of Table/Figure	
1.	BASELINE	
1.1.	Study Information	
	1.1.1.	Study Information
1.2.	Disposition of Patients	
	1.2.1	Screen Failures
	1.2.2	Number of Subjects Randomized by Site
	1.2.3	Disposition of subjects
	1.2.4	Analysis Sets
1.3.	Consort Study Flowchart	
	Fig .1.3.1	Consort Flowchart
1.4.	Baseline characteristics	
	1.4.1	Demographic Characteristics
	1.4.2	Clinical-Pathological Characteristics
	1.4.3	Local Laboratory Biomarkers
	1.4.4	Baseline Lesions
	1.4.5	Stratification Factors

1.5.	Medical History	
	1.5.1	Medical History by Preferred Term
	1.5.2	Most common (at least 5%) Medical and Surgical History by Preferred Term ITT Population
1.6.	Concomitant Treatments	
	1.6.1	Concomitant Medications by Standardized Medication Name Safety Population
	1.6.2	Most common concomitant medications (at least 10% overall) by Standardized Medication Name Safety Population
1.7.	Previous Treatments	
	1.7.1	Prior Therapies for BC
	1.7.2	Previous Treatment for Early BC.
	1.7.2	Previous Treatment for MTX BC.
1.8.	Study Drug Exposure	
	1.8.1	Summary of Study Drug Exposure
	1.8.2	Summary of Dose Modifications
1.9.	Subsequent Therapies	
	1.9.1	Subsequent Therapies for BC
	1.9.2	Subsequent Chemotherapy for BC
	1.9.3	Subsequent Hormone therapy for BC
	1.9.4	Subsequent Targeted therapy for BC
2.	EFFICACY	
2.1.	Overall Response Rate	
	2.1.1	Summary of Overall Response Rate Efficacy population

	2.1.2	Summary of Overall Response Rate ITT population
2.2.	Progression-free Survival	
	2.2.1	Progression-free Survival Efficacy population
	Fig . 2.2.1	Progression-free Survival Efficacy population
	2.2.2	Progression-free Survival ITT population
	Fig . 2.2.2	Progression-free Survival ITT population
2.3.	Overall Survival	
	2.3.1	Overall Survival Efficacy population
	Fig . 2.3.1	Overall Survival Efficacy population
	2.3.2	Overall Survival ITT population
	Fig . 2.3.2	Overall Survival ITT population
3.	SAFETY	
3.1.	Treatment Emergent Adverse Event	
	3.1.1	Overview of Treatment-Emergent Adverse Events
	3.1.2	Treatment-Emergent Adverse Events by System Organ Class and Preferred Term
	3.1.3	Drug-Related Treatment-Emergent Adverse Events by System Organ Class and Preferred Term
	3.1.4	Grade 3 or Higher Treatment-Emergent Adverse Events by System Organ Class and Preferred Term
	3.1.5	Grade 3 or Higher Drug-Related Treatment-Emergent Adverse Events by System Organ Class and Preferred Term
	3.1.6	Most common (at least 10% in any treatment arm) Treatment-Emergent Adverse Events by Preferred Term
	3.1.7	Serious Treatment-Emergent Adverse Events by System Organ Class and Preferred Term Safety Population

	3.1.8	Serious Drug-Related Treatment-Emergent Adverse Events by System Organ Class and Preferred Term Safety Population
	3.1.9	Treatment-Emergent Adverse Events by Grade
	3.1.10	Drug-Related Treatment-Emergent Adverse Events by Grade
	3.1.11	Serious Treatment-Emergent Adverse Events by Grade
	3.1.12	Adverse Events from Laboratory according NCI CTC v4.03 by System Organ Class and Preferred Term
3.1.	Deaths	
	3.2.1	All-Cause Mortality Safety Population
4	OTHER ENDPOINTS	
	4.1	Changes of germline methylation pre and post treatment
	4.2	Correlation between germline methylation status and efficacy outcome data
	4.3	Correlation between germline methylation status and somatic methylation status
	4.4	Correlation of methylation between primary and metastatic lesions
	4.5	Correlation between expression data and promoter methylation status of BRCA1/2 and outcome data
5	EXPLORATORY OBJECTIVES (if performed)	
	5.1	Exploratory biomarkers of response or resistance to Olaparib
	5.2	Review potential pharmacogenomics analyses related to drug response or adverse drug reactions
	5.3	Specific mutations or epigenetic biomarkers identified in pre-therapy tumour specimens as potentially linked to treatment response

*The numbers of tables and figures do not have to match exactly with those of the statistical report. The feasibility and interest of performing some of the described tables and figures based on the available number of patients, data and biological samples.*

*Please see Shells Tables, Listings and Figures.*

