There are other causes leading deficiencies in the repair process of double-stranded DNA breaks by the homologous recombination mechanism, such as the loss of heterozygosity or the expression of negative regulators of BRCA, as ID4, or loss of function of proteins as RAD51, CHECK2 or ATM⁴¹.

The methylation assessment can be performed both at tumour tissue and at germline level (DNA from nucleated peripheral blood cells), without necessarily existing a correlation between both measurements. Furthermore, methylation status is a changing and dynamic process, determined at tumour level by the own carcinogenic process and at germline level by multiple processes, including the different anti-tumour treatments.

The methylation status of *BRCA1* promoter assessed in germline DNA, isolated from peripheral blood cells, has been associated with breast cancer risk^{42,43,44}. In the Bosviel dataset the methylation rate of *BRCA1* at the germline level in breast cancer patients (n=902) was 47.1%⁴⁵. These results are consistent with other datasets such as those studied by Snell⁴⁶ or Iwamoto who detected methylation of *BRCA1* promoter in 43 out of 200 breast cancer patients (21.5%), a higher frequency than the rate observed in controls (27/200, 13.5%)⁴⁷. These findings suggest that *BRCA1* promoter methylation is an event that occurs in normal tissues and can be associated with the development of breast cancers *BRCA1*-like⁴⁸.

Although there is limited information, the relationship between the methylation status in *BRCA1* promoter in germline and tumour DNA has been reported in several datasets^{38,49}. According to Wong et al⁴⁹, this association suggest that the methylation at this level and in a constitutive manner could be the first event in the carcinogenesis process of a group of non-inherited breast cancers. Other authors have reported this correlation between germline and tumour methylation status, as Al-Moghrabi et al. who found correlation in 10 out of 15 analysed cases (66.7%)⁵⁰. Sarah et al. showed that blood DNA methylation levels correlated with tumour methylation at most of the *BRCA1* CpG sites examined although those levels were higher in tumour DNA compared to matched blood DNA samples³⁸.

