Haematological toxicity: Anaemia and other haematological toxicities are generally low grade (CTCAE Grade 1 or 2), however, there are reports of CTCAE Grade 3 and higher events. Anaemia was the most common CTCAE Grade ≥ 3 adverse reaction reported in clinical studies. Median time to first onset of anaemia was approximately 4 weeks (approximately 7 weeks for CTCAE Grade ≥ 3 events). Anaemia was managed with dose interruptions and dose reductions, and where appropriate with blood transfusions. In clinical studies the incidences of dose interruptions, reductions and discontinuations for anaemia were 8.3%, 5.0% and 0.8%, respectively. An exposure-response relationship between olaparib and decreases in haemoglobin has been demonstrated. In clinical studies with olaparib, the incidence of CTCAE Grade ≥ 2 shifts (decreases) from baseline in haemoglobin was 20%, absolute neutrophils 15%, platelets 5%, lymphocytes 30% and leucocytes 20% (all % approximate). The incidence of elevations in MCV from low to normal at baseline to above the upper limit of normal was approximately 55%. Levels appeared to return to normal after treatment discontinuation and did not appear to have any clinical consequences.

Baseline testing, followed by monthly monitoring of complete blood counts is recommended for the first 12 months of treatment with olaparib, and periodically after this time to monitor for clinically significant changes in any parameter during treatment which may require dose interruption or reduction and/or further treatment.

Other laboratory findings: In clinical studies with olaparib the incidence of CTCAE Grade ≥ 2 shifts (elevations) from baseline in blood creatinine was approximately 15%. Data from a double-blind placebo controlled study showed median increase up to 23% from baseline remaining consistent over time and returning to baseline after treatment discontinuation, with no apparent clinical sequelae; 90% of patients had creatinine values of CTCAE Grade 0 at baseline and 10% were CTCAE Grade 1 at baseline.

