- **Haematology:** Full haematology assessments for safety (haemoglobin, red blood cells [RBC], platelets, mean cell volume [MCV], mean cell haemoglobin concentration [MCHC], mean cell haemoglobin [MCH], white blood cells [WBC], absolute differential white cell count [neutrophils, lymphocytes, monocytes, eosinophils and basophils] and absolute neutrophil count or segmented neutrophil count and band forms) should be performed at each visit and when clinically

indicated. If absolute differentials are not available % differentials should be provided. Study visits for safety assessments will be scheduled on baseline visit and day 8 (+/- 3 days) of cycle 1 and in subsequent cycles every 28 days (+/- 7 days). This analysis should be performed also in the 30-day post-discontinuation follow-up evaluation performed 30 days (+/- 7 days) following the discontinuation of study treatment. In case the beginning of this new therapy cannot be delayed as per the investigator's judgment, the safety visit may be performed in advance, but always before starting with the new anticancer therapy.

If treatment is discontinued close to the theoretical date for the next cycle and it is not planned to perform in advance the post-treatment visit due to the initiation of a new anticancer therapy, a new haematology analysis should be performed at the moment of the study treatment discontinuation.

- **Coagulation testing:** Activated partial thromboplastin time (aPTT) and international normalised ratio (INR) will be performed at baseline and if clinically indicated unless the patient is receiving warfarin. Patients taking warfarin may participate in this study; however, it is recommended that prothrombin time (INR and aPTT) be monitored carefully at least once per week for the first month, then monthly if the INR is stable.
- **Blood Chemistry:** sodium, potassium, calcium, magnesium, fasting glucose, creatinine, total bilirubin, gamma glutamyltransferase (GGT), alkaline phosphatase (AP), aspartate transaminase (AST), alanine transaminase (ALT), urea or blood urea nitrogen (BUN), total protein, albumin and lactic dehydrogenase (LDH) should be performed.

In case a subject shows an AST **or** ALT $\geq 3 \times$ ULN **or** total bilirubin $\geq 2 \times$ ULN please refer to Appendix 5 "Actions required in cases of combined increase of Aminotransferase and Total Bilirubin – Hy's Law", for further instructions.

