u	One blood sample (EDTA) to analyse BRCA mutational status must be sent to Myriad laboratories, unless test have been done previously at Myriad and absence of mutations has been already determined. It could be sent once signed the ICD 1) in the previous line of treatment, once inclusion/exclusion criteria have been reviewed and the patient is considered a potential candidate to the study or 2) after ending the previous line of treatment, during screening procedure (see section 6.3 for further instructions).
v	Whole blood samples (EDTA and tubes optimized for RNA isolation) will be collected at screening and at the end of treatment to assess germline methylation status and/or expression levels of BRCA genes as well as to perform other exploratory analyses . Sample after treatment must be taken at the end of study treatment prior to initiation of next therapy regimen. If a patient end the treatment due to other cause different to disease progression, collect other sample once progression is documented (although initiated other treatment), if available.
w	Plasma samples will be obtained at screening (solicited to all screened patients) and during treatment (one sample taken between 4 to 6 week of treatment, preferable prior to receive the treatment) and at the end of study treatment prior to initiation of next therapy regimen (only enrolled patients). If a patient end the treatment due to other cause different to disease progression, collect other sample once progression is documented (although initiated other treatment), if available.
y	Tumour Tissue for Biomarker Assessments: If available, tumour tissue (FFPE) from primary tumour (solicited to all screened patients) and metastatic lesions at disease progression (only enrolled patients) will be collected for retrospective biomarker assessments. Samples will be sent to the sponsor-designated central laboratories. If a patient end the treatment due to other cause different to disease progression, collect this once progression is documented (although initiated other treatment), if available.

	This post-treatment visit must be performed before starting with any new anticancer therapy; however, in case the beginning of this new therapy cannot be delayed as per the investigator's judgment, the safety visit may be performed in advance, but always before starting with the new anticancer therapy.
-------------------------------------	---

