### **9.2.3      *BRCA1/2* Methylation and expression analysis**

**To explore changes in the methylation status of *BRCA1/2* promoter in germline DNA prior and after treatment discontinuation.**

The methylation status of the *BRCA1* and *2* promoters will be measured in germline DNA from blood cells collected at the beginning of the study and after disease progression or at the end of study treatment for other cause, and in paired primary and metastatic lesions. Methylation status will be provided as a continuous (the methylation value will be obtained from the average of the CpG dinucleotides included in the sequence analysed) and also as a binomial variable (status methylated or not methylated).

If methylation status is a continuous variable, to compare the value of methylation between prior and after treatment, the difference of these values will be used and will be used statistical t (student-Fisher) or Wilcoxon test depending if it must be used a parametric or non-parametric test.

If methylation status is a binomial variable, to compare the value of methylation between prior and after treatment it will be used the McNemar test or exact binomial test.

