#### **To correlate *BRCA1/2* expression with efficacy parameters:**

mRNA levels of *BRCA1* and *2* will be assessed in blood and available tumour samples. Expression data will be given as a continuous or as a binomial variable.

To evaluate the effect of *BRCA1/2* expression with time to event variables (PFS, OS) it will be used a univariate Cox Regression model.

To evaluate the effect of *BRCA1/2* expression with efficacy rate parameters it will be used chi-square test if both of them are quantitative, and will be used an ANOVA analysis if one variable is quantitative and the other one are qualitative.

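### The pre/post test of blood BRCA1/2 methylation ignores white-cell composition, so a shift in cell mix could, if cell types differ in methylation, appear as a methylation change

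*SAP*

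**What the plan says.** Protocol Attachment 1 (footnote v) sets the specimen: "Whole blood samples (EDTA and tubes optimized for RNA isolation) will be collected at screening and at the end of treatment to assess germline methylation". Protocol 1.2.2 describes the germline measurement as "DNA from nucleated peripheral blood cells". Cell sorting is not mentioned in either document.

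Under SAP 9.2.3 each sample yields one value per promoter, averaged over CpG sites, and also a methylated/unmethylated status. For the continuous value before and after treatment, "the difference of these values will be used and will be used statistical t", or a Wilcoxon test. For the binary status the plan names McNemar or an exact binomial test. None of these has a covariate. SAP section 10 reports the result in table 4.1, of which only the title is given: "Changes of germline methylation pre and post treatment".

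Protocol 1.4.5.3 gives the approximate incidence of grade 2 or worse falls from baseline on olaparib, including "absolute neutrophils 15%, platelets 5%, lymphocytes 30% and leucocytes 20"%. Protocol 6.2.1 requires haematology with "absolute differential white cell count [neutrophils, lymphocytes, monocytes, eosinophils and basophils" at baseline, during treatment and at the post-treatment visit. No methylation analysis uses these counts.

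**The concern.** A whole-blood methylation value is a weighted mean of the values in each cell type, with the cell shares as weights. If the shares move between the two draws and the cell types differ in methylation, the mean moves even though no cell's methylation has changed. The paired test on the raw difference cannot tell the two apart.

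Pre/post change in germline methylation is a named secondary objective. Protocol 1.2.2 says that methylation at this level is determined by several processes, anti-tumour treatment among them, so a significant result invites a reading as a treatment effect within cells. The data that would help to check that reading are already collected but have no place in the plan.

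**Working it through.** The documents give no sample size, SD or expected change for this test, so there is no planned figure to reproduce. The check has two parts.

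**1. Do the lineages fall together?** From Protocol 1.4.5.3, at least 30% − 15% = 15% of patients have the lymphocyte fall without the neutrophil fall. Applied to 31 evaluable patients this is 0.15 × 31 = 4.65, about 5. These are shares of patients with falls in absolute counts, so a shift in mix is an inference and not a reported result.

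**2. What could a shift do to the test?**

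From the documents: 5% two-sided level (SAP 9.1); 31 evaluable patients, or 12 if the trial stops at stage 1 (SAP 3.1).

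Assumed, because the documents give no values:
- 28 usable pairs (31 × 0.9 = 27.9, as if one pair in ten were lost);
- SD of the paired change, 2 to 4 methylation points;
- difference in methylation between lymphocytes and other white cells, *d* = 0, 5 or 10 points;
- mean shift in lymphocyte share, *s* = 3.2 or 10 points.

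The 3.2 is built as follows. Take lymphocytes at 1.5 of 6.0 × 10⁹/L, a share of 25%. Halve them with other cells unchanged: 0.75/5.25 = 14.3%, a fall of 10.7 points. If 30% of patients have that fall and the rest none, the mean shift is 0.30 × 10.7 = 3.2 points. A mean of 10 points needs roughly that fall in every patient.

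Formulas, with no true change in any cell:
- apparent change = *d* × *s*/100;
- noncentrality = apparent change / (SD/√28), with √28 = 5.29;
- rejection rate from the noncentral t with 27 df.

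Example: *d* = 10, *s* = 10 gives an apparent change of 1.0 point. With SD 2 the noncentrality is 1.0/(2/5.29) = 2.65 and the rejection rate is 72%. With SD 4 it is 1.32 and 25%.

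| *d* (points) | *s* (points) | apparent change | rejection, SD 4 | rejection, SD 2 |
|---|---|---|---|---|
| 0 | any | 0 | 5% | 5% |
| 5 | 3.2 | 0.16 | 5.5% | 6.9% |
| 10 | 3.2 | 0.32 | 7% | 13% |
| 5 | 10 | 0.50 | 10% | 25% |
| 10 | 10 | 1.00 | 25% | 72% |

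With 12 pairs, *d* = 10 and *s* = 10 give 12% to 35%. No figure was calculated for the McNemar form.

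**Cost of adjusting.** With one covariate of mean *m* and SD *v*, and the same residual SD, the standard error of the intercept relative to that of the plain mean is about √(1 + n·m²/((n − 1)·v²)). With *m* = 10 and an assumed *v* = 8, this is √(1 + (28/27) × 100/64) = 1.62 for 28 pairs and √(1 + (12/11) × 100/64) = 1.64 for 12. With *m* = 3.2 and 28 pairs it is 1.08. Simulation with two covariates under the large shift gave intervals about 1.6 to 1.7 times as wide with 28 pairs and about 1.8 to 2.0 times with 12.

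**The case against.** The strongest reply is that the key premise is not in the documents. They do not say that BRCA1/2 promoter methylation differs between white-cell types, and with no difference the test keeps its 5% error rate. Protocol 1.2.2 even cites a view of blood methylation as constitutive; that does not exclude differences between cell types, but does not support them. This stands, and it makes the whole point conditional.

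A reader might infer that olaparib is known to shift the cell mix. Protocol 1.4.5.3 does not show that: it reports falls in absolute counts during treatment, not proportions, and not counts at the end-of-treatment draw. Parallel falls leave the mix unchanged, and a neutrophil fall alone raises the lymphocyte share.

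A reader might also take 72% as the expected error rate. It needs a mean 10-point shift across all patients together with a 10-point difference between cell types.

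A further inference would be that the same fault affects blood mRNA, which "will be assessed in blood and available tumour samples". The SAP analysis there relates expression to efficacy and is not a pre/post test, so the argument does not carry over.

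It is also fair to say that the objective is only to explore change, and that a shift in the whole-blood average is a real change in the measure as defined. That supports careful labelling. It does not remove the value of showing whether cell mix explains the change. SAP 9.2.3 allows additional biomarker analysis where appropriate, but commits to none, and an adjustment chosen after seeing the result would be weak. The table shells are a separate document and were not available.

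**Conclusion.** The omission is confirmed: a bulk whole-blood average is tested before and after a drug that lowers white-cell counts, with no allowance for composition, although a differential count is collected. Whether this biases the result is not established. Under the stated assumptions the rejection rate with no within-cell change runs from 5% to 72%, and from about 5% to 13% if the mean shift in share is about 3 points. The documents do not support a claim that the planned test is materially biased. They do support saying that, as planned, a significant result could not be attributed to a change within cells.

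The scope is one secondary objective. With no control arm, time and progression are also mixed into any pre/post change, and adjustment for cell mix would not cure that.

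**What to change.** In SAP 9.2.3, with table 4.1 to match:

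- Keep the planned paired t/Wilcoxon and McNemar/exact analyses, labelled as change in whole-blood methylation.
- Beside the continuous result, add a pre-specified sensitivity analysis: regress the change in methylation on the change in lymphocyte share and report the intercept with its interval. Add the change in neutrophil share only if the trial goes past stage 1.
- Use the differential nearest each blood draw and report the time gap. Cycle visits are every 28 days ± 7, and a count at discontinuation is required only in some cases, so the two may not coincide. Mistimed shares leave some confounding in the intercept.
- State that a change will not be read as a within-cell effect unless the adjusted estimate agrees, and that with no control arm neither analysis isolates a drug effect.

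The regression does not extend to the McNemar analysis, which relies on the labelling alone. The cost is SAP wording, with no new samples or visits. The adjusted interval will be wider: little changed if the mean shift is small, but possibly up to about twice as wide with 12 pairs, which is why only one covariate is proposed at that size.
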